16. STATISTICAL CONSIDERATIONS

16.1 Determination of Sample Size

The primary endpoint of the study is the overall response rate to crenolanib. The outcome may be different for patients with or without the previous FLT3 TKI therapy. Therefore, patients will be stratified according to whether they have recurred after prior chemotherapy without a FLT3 TKI treatment or they have progressed after prior therapy with a FLT3 TKIs.

Based on the promising results observed to date, the sample size for each cohort will be expanded to include a total of 30 patients in Cohort A and 40 patients in Cohort B. Such additional patients will permit a more accurate assessment of the efficacy and safety of crenolanib in these populations. The total sample size for the two cohorts is 70 patients.

Cohort B (N=40): Two parallel Simon minimax two-stage Phase II designs will be used for the two cohorts of patients. For the patients who progressed after prior chemotherapy with FLT3 TKI, the null response rate will be 5%, and target response rate will be 20%. With alpha of 0.05 and beta of 0.08, the first stage will require 28 patients. If there is 1 or no patient responding, the trial will be stopped. If 2 or more out of the first 28 patients respond, accrual will continue until a total of 40 patients have been enrolled. At the end of the study, if 5 or more patients out of 40 respond, the regimen will be considered active. With this design, the probability of early termination is 59% if the true response rate is only 5%.

Cohort A (N=30): For the patients who progressed after prior chemotherapy without FLT3 TKI, the null response rate will be 5%, and target response rate will be 30. With alpha of 0.06 and beta of 0.01, the first stage will require 24 patients. If there is 1 or no patient experiencing the response, the trial will be stopped. If 2 or more out of the first 24 patients respond, accrual will continue until a total of 30 patients have been enrolled. At the end of the study, if 4 or more patients out of 30 respond, the regimen will be considered active. With this design, the probability of early termination is 66% if the true response rate is only 5%.

The method of Thall, Simon, and Estey will be employed to perform interim safety monitoring. We will assume a Beta (0.6, 1.4) prior distribution for the toxicity rate which in particular has mean of 30%. The toxicity is defined as any grade 3 or greater non-hematologic toxicities attributed to the study drug.

The following decision criteria will be applied continuously up to the 70 patient. The two cohorts of patients will be jointly monitored for the safety. Targeting a 30% toxicity rate as a trade-off, the trial will be stopped early according to the following monitoring rule.

Pr{toxicity rate > 30% | data} > 0.93

That is, if at any time during the study we determine that there is more than a 93% chance that the toxicity rate is more than 30% we will stop the study.

The design software Multc Lean Desktop (version 2.1) developed by the Department of Biostatistics at M. D. Anderson Cancer Center (MDACC) was used to generate the toxicity stopping boundaries and the OC table. The stopping rule boundary is shown in table 16.1.

Table 16.1 Safety monitoring boundary

#patient	Stop the trial if there are this
	many toxicities total:
5	4-5
10	6-10
15	8-15
20	10-20
25	12-25
30	14-30
35	15-35
40	17-40
45	19-45
50	21-50
55	22-55
60	24-60
65	26-65

The operating characteristics of this rule in the trial are shown in the following table

Table 16.2 The operating characteristics

True toxicity	Early Stopping Probability	Average number of patients treated
0.2	0.02	69.1
0.25	0.06	67.0
0.3	0.18	61.8
0.35	0.42	52.2
0.4	0.71	39.9
0.5	0.98	20.4

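### The toxicity rule is written for continuous monitoring, but Table 16.2 gives the operating characteristics of looks after every 5 patients

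*Combined protocol and SAP*

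**What the plan says.** The safety monitoring text is in protocol section 16.1. Toxicity is any grade 3 or worse non-hematologic toxicity attributed to crenolanib. The prior for its rate is Beta(0.6, 1.4), with mean 30%, and the trial stops when "Pr{toxicity rate > 30% | data} > 0.93".

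On frequency, the section says: "The following decision criteria will be applied continuously up to the 70 patient". The sentence after the formula repeats this, saying the study stops if the criterion is met at any time. On scope: "The two cohorts of patients will be jointly monitored for the safety".

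Two tables follow. "The stopping rule boundary is shown in table 16.1", and that table has rows only at 5, 10, ..., 65 patients. Table 16.2 is introduced with "The operating characteristics of this rule in the trial are shown in the following table". Neither the text nor the table captions say that the rule is checked, or was evaluated, only after every 5 patients.

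**The concern.** A sequential rule that is checked more often stops more often and earlier. Table 16.1 lists only multiples of 5, which suggests that the software was run with looks every 5 patients. If so, Table 16.2 understates how often the written rule stops the trial and overstates the average number treated.

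Two things are at stake. First, anyone judging the design from Table 16.2 would be reading figures for a different rule. Second, the two readings can give opposite instructions on the same data. After 3 toxicities in 4 patients the written criterion is met. Table 16.1 has no row for 4 patients, and its row for 5 requires 4 toxicities, so if the fifth patient has none, the table says continue. A stop ends both cohorts, so the look schedule also affects the chance that either efficacy test is completed.

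**Working it through.** **Inputs, all from section 16.1.** Prior Beta(0.6, 1.4); stop if the posterior probability of a rate above 0.30 exceeds 0.93; at most 70 patients; both cohorts pooled.

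**Boundary.** With k toxicities in n patients the posterior is Beta(0.6 + k, 1.4 + n − k). The boundary at n is the smallest k for which Pr(p > 0.30) > 0.93.

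- n = 5: k = 3 gives 0.8745 and k = 4 gives 0.9751, so the boundary is 4.
- n = 30: k = 13 gives 0.9286 and k = 14 gives 0.9666, so the boundary is 14.

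All 13 rows of Table 16.1 are reproduced (4, 6, 8, 10, 12, 14, 15, 17, 19, 21, 22, 24, 26). The posterior rule and the printed boundaries are therefore correct.

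**Operating characteristics.** For a true rate p, carry the distribution of the toxicity count forward one patient at a time: P(n, k) = (1 − p)·P(n−1, k) + p·P(n−1, k−1). At each look, remove the probability at or above the boundary. The early-stopping probability is the sum of the mass removed. The mean N is the sum of n × mass removed at n, plus 70 × the mass never removed. This is exact, with no simulation.

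Early-stopping probability / mean N:

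| True rate | Table 16.2 | Looks at 5, 10, ..., 65 | Every patient, 1–69 | Every patient, 5–69 |
|---|---|---|---|---|
| 0.20 | 0.02 / 69.1 | 0.016 / 69.1 | 0.048 / 67.0 | 0.033 / 68.0 |
| 0.25 | 0.06 / 67.0 | 0.059 / 67.0 | 0.121 / 63.1 | 0.101 / 64.5 |
| 0.30 | 0.18 / 61.8 | 0.183 / 61.8 | 0.280 / 55.6 | 0.259 / 57.4 |
| 0.35 | 0.42 / 52.2 | 0.423 / 52.2 | 0.535 / 44.4 | 0.519 / 46.2 |
| 0.40 | 0.71 / 39.9 | 0.705 / 39.9 | 0.790 / 31.9 | 0.782 / 33.5 |
| 0.50 | 0.98 / 20.4 | 0.979 / 20.4 | 0.990 / 14.7 | 0.989 / 15.9 |

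The five-patient schedule matches all 12 entries at the printed rounding. Looks every 1, 2, 3, 4 or 10 patients do not reproduce the whole table. Nor do five-patient looks with a further look at 70, which give a stopping probability of 0.456 at a rate of 0.35 and 0.746 at 0.40.

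**Size at 30% toxicity.** Relative to the five-patient schedule, the excess stopping probability is:

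- looks from patient 1: 0.280 − 0.183 = 0.097
- looks from patient 5: 0.259 − 0.183 = 0.076
- looks from patient 10: 0.235 − 0.183 = 0.052

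**Between the printed rows.** The same formula gives boundaries that Table 16.1 does not show. For example, 3 of 3 gives 0.976 and 3 of 4 gives 0.935, and both meet the criterion.

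**Effect on Cohort B.** This was simulated with 20,000 trials per scenario, toxicity independent of response, the two cohorts accruing interleaved, and a safety stop counted as not declaring activity. At a 20% response rate and 25% toxicity, the chance that Cohort B is completed and declared active is about 0.92 with no safety rule, 0.87 with looks every 5 patients and 0.81 with looks after each patient.

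**The case against.** The strongest reply is that Table 16.2 contains no calculation error. It is exactly right for the boundary in Table 16.1, which the section itself calls the stopping boundary, so the fault could equally lie in the wording on frequency. That is a fair description, and it is why either side can be corrected. It does not remove the contradiction, because the text states continuous application twice and attributes Table 16.2 to that rule.

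Other points limit the size of the finding:

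- The 10-point excess at 30% assumes looks from patient 1 with each outcome known at the look. Later first looks reduce it to about 8 or 5 points, and delayed outcomes would make truly continuous looks hard to achieve.
- The plan calls 30% a trade-off rate, so whether a stop there is a false stop is a matter of judgement.
- At 50% toxicity the stopping probability hardly changes (0.98 against 0.99), although the mean N does (20.4 against 14.7).
- The unprinted boundaries follow from the prior and cutoff, so printing them is a convenience for those applying the rule.
- Of the 11-point fall in Cohort B success, from 0.92 to 0.81, about 5 points arise under five-patient looks as well. Only the remaining 6 or so are due to the look schedule. The plan states power for each Simon design separately and claims no joint figure.
- This version expands an ongoing study, so some early looks may already have passed. The number treated in this study alone is not given, so the remaining stopping risk cannot be computed.

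All of these stand as limits on magnitude. None makes Table 16.2 describe the rule as written.

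**Conclusion.** The concern holds. The rule described in section 16.1 does not have the operating characteristics in Table 16.2. Those belong to looks after every 5 patients with the last at 65, a schedule inferred from the exact match on all 12 entries and the spacing of Table 16.1. Under continuous looks from patient 1, the early-stopping probability is 10 percentage points higher than stated at a true rate of 30%, twice the stated value at 25%, and 8 points higher at 40%. At 40% the mean number treated also falls by 8 (31.9 against 39.9). The direction is the same for continuous looks starting at patient 5 or 10.

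These figures assume that each patient's toxicity outcome is known when the look is made. The Cohort B effect, about 6 points at 25% toxicity, also rests on the simulation assumptions listed with it. The mismatch casts no doubt on the posterior criterion or on the printed rows of Table 16.1. It should be corrected because it misstates the design's stopping risk and leaves the stopping decision ambiguous between multiples of 5.

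**What to change.** Make the frequency wording in section 16.1 and the two tables agree, in one of two ways:

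1. State that the criterion is evaluated after every 5 patients, at 5, 10, ..., 65, and remove the wording about continuous, any-time application. Tables 16.1 and 16.2 then stand unchanged. This costs one sentence.
2. Keep continuous monitoring, state the first patient count at which it applies, extend Table 16.1 to every patient count, and replace Table 16.2 with the corresponding values. For looks from patient 1 these are the figures in the every-patient column (1–69) of the comparison table. This costs one rerun of the design software, and the published stopping probabilities become less favourable.

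In either case, say how patients whose toxicity outcome is still pending are counted at a look, because all of these figures assume that outcomes are known.

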9. TREATMENT PLAN

9.1 General

The study will enroll patients with primary AML relapsed/ refractory after prior therapy, secondary AML (due to prior chemo- or radiation therapy) or prior transformed MDS/MPN with FLT3 activating mutations. Patients will be treated with crenolanib three times daily, preferably every eight hours, continuously until they fulfill one of the criteria for study discontinuation. The objective will be to administer crenolanib at full dose starting at 100 mg TID. Other dose levels will be used for dose adjustments for toxicity (refer to section 10) during therapy. The only exception to this will occur on course 1 day 1, when doses 2 and 3 will be held in order to analyze the pharmacokinetics of the first dose administered out to 24 hours.

Patients currently enrolled at 100mg TID (protocol v1.1) may be dose escalated based on BSA, see table 10.2.

Up to 70 evaluable patients will be enrolled on this study: 30 patients in Cohort A and 40 patients in Cohort B. Patients receiving less than 28 days of study dug will be replaced for efficacy evaluation. All patients will be assessed for toxicity.

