9.3 Crenolanib Administration

- Prophylactic antiemetic therapy is recommended to be used as needed for nausea and/or vomiting.
- If a dose is missed or vomited, it should not be taken again. The next dose should not be increased to account for missing a dose. The patient should take the next regular dose at the regularly scheduled time.

9.4 **Duration of Therapy**

Treatment may continue until one of the following criteria applies:

- 1. Clinically significant progressive disease, or
- 2. Intercurrent illness that in the opinion of the investigator prevents further administration of treatment, or
- 3. Patient request, or
- 4. General or specific changes in the patient's condition render the patient unacceptable for further treatment in the judgment of the investigator, or
- 5. Unacceptable toxicity that in the opinion of the investigator makes it unsafe to continue therapy, or
- 6. Treatment interruption due to toxicity that has not recovered to at least grade 1 within 8 weeks

It is planned that up to a total of 12 cycles of therapy will be administered for patients deriving benefit from this regimen. Continuation of therapy for patients completing 12 cycles of therapy may be considered on a case by case basis after discussion with the sponsor's medical monitor.

A minimum of 1 full course (defined as the administration of crenolanib for 28 days) will be required for a patient to be considered as having received an adequate trial to evaluate efficacy. Patients who do not complete one cycle of crenolanib therapy will be replaced. All patients receiving at least one dose of study drug will be considered evaluable for toxicity.

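### The toxicity stopping rule is capped and calibrated at 70 patients, but 70 is the evaluable target: with replacements, dosed patients after the 70th lie beyond the cap, and the text conflicts on whether monitoring continues

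*Combined protocol and SAP*

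**What the plan says.** Section 16.1 sets a Bayesian monitor for grade 3 or greater non-hematologic toxicity attributed to the study drug. The prior is stated as: "We will assume a Beta (0.6, 1.4) prior distribution for the toxicity rate which in particular has mean of 30" percent. The study stops when "Pr{toxicity rate > 30% | data} > 0.93". The count is pooled: "The two cohorts of patients will be jointly monitored for the safety". Its reach is given as: "The following decision criteria will be applied continuously up to the 70 patient".

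Table 16.1 lists the boundary every five patients, ending at 26 toxicities in 65. Table 16.2 gives early-stopping probabilities and average numbers treated. Section 16.1 puts the total sample size at 70 and makes no allowance for replacements.

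Section 9.1 counts differently: "Up to 70 evaluable patients will be enrolled on this study: 30 patients in Cohort A and 40 patients in Cohort B". It continues: "Patients receiving less than 28 days of study dug will be replaced for efficacy evaluation. All patients will be assessed for toxicity". Section 9.4 also replaces patients who do not finish one cycle, and adds: "All patients receiving at least one dose of study drug will be considered evaluable for toxicity".

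Two statements carry no cap. The sentence after the criterion in 16.1 restates the rule as operating throughout the study. The Statistical Methods part of the synopsis stops accrual whenever unacceptable toxicity is seen in more than 30% of patients.

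**The concern.** The safety rule and the enrolment target use the same number, 70, for different sets of patients. For enrolment it is the number evaluable for efficacy. For toxicity the denominator is everyone dosed, which is 70 plus the replacements once both cohorts are full. One replacement is then enough to pass the cap.

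Patients who stop early because of toxicity are among those replaced, so more early toxicity means more patients dosed after the 70th. Anyone monitoring safety at, say, the 75th patient has no boundary row, no operating characteristics, and two instructions that disagree on whether the rule still applies.

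Counting only the 70 evaluable patients would keep the number within the cap. It would also drop from the toxicity count the patients who stopped early, including those who stopped for toxicity, and so contradict 9.1 and 9.4.

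**Working it through.** **Inputs.** Prior Beta(0.6, 1.4), threshold 0.30 and cut-off 0.93 (section 16.1); boundary and operating characteristics (Tables 16.1 and 16.2); 70 evaluable patients with replacement (sections 9.1 and 9.4). The replacement rate r is not in the documents and is assumed to be 10%, 20% or 30%.

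**Step 1: reproduce Table 16.1.** With x toxicities in n patients the posterior is Beta(0.6 + x, 1.4 + n − x). The boundary is the smallest x for which the posterior probability of a rate above 0.30 exceeds 0.93. At n = 65, x = 26 gives 0.952 and x = 25 gives 0.921, so the boundary is 26, as stated. All 13 rows agree.

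**Step 2: reproduce Table 16.2.** Exact binomial recursion, looks every 5 patients from 5 to 65, maximum 70 treated:

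| True rate | Stop, stated | Stop, computed | Average N, stated | Average N, computed |
|---|---|---|---|---|
| 0.20 | 0.02 | 0.016 | 69.1 | 69.1 |
| 0.25 | 0.06 | 0.059 | 67.0 | 67.0 |
| 0.30 | 0.18 | 0.183 | 61.8 | 61.8 |
| 0.35 | 0.42 | 0.423 | 52.2 | 52.2 |
| 0.40 | 0.71 | 0.705 | 39.9 | 39.9 |
| 0.50 | 0.98 | 0.979 | 20.4 | 20.4 |

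The table is right for a maximum of 70 treated, so replacements were not modelled. At a true rate of 0.20, a maximum of 78, 88 or 100 treated would give an average of 76.9, 86.8 or 98.6, against the stated 69.1.

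**Step 3: number treated.** N = 70/(1 − r), rounded up: 70/0.9 = 77.8, so 78; 70/0.8 = 87.5, so 88; 70/0.7 = 100. That is 8, 18 or 30 patients after the 70th.

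**Step 4: extend the boundary.** The same prior and cut-off give 27/70, 29/75, 31/80, 33/85, 34/90, 36/95 and 38/100.

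**Step 5: value of continuing past 70.** The stated cap permits a look at 70, although Table 16.1 has no row for it, so the fair baseline is stopping by n = 70 and not by 65. Looks stay every 5 patients and end before the last patient (75; 85; 95):

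| True rate | Stopped by 70 | N = 78 | N = 88 | N = 100 |
|---|---|---|---|---|
| 0.20 | 0.016 | 0.016 | 0.016 | 0.016 |
| 0.30 | 0.195 | 0.199 | 0.205 | 0.215 |
| 0.35 | 0.455 | 0.469 | 0.488 | 0.520 |
| 0.40 | 0.746 | 0.764 | 0.788 | 0.825 |
| 0.50 | 0.988 | 0.990 | 0.994 | 0.997 |

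At 0.40 the gain is 1.8, 4.2 or 7.9 points. As a share of trials not yet stopped at 70, (0.764 − 0.746)/(1 − 0.746) = 7%, and likewise 16% and 31%.

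**The case against.** The strongest reply is that a rule still exists. The restatement in 16.1 has no cap, the posterior can be computed at any n, and the synopsis has its own uncapped accrual stop. A reader might infer from the cap that later patients have no stopping rule at all, or that the Bayesian rule is the only study-level safety stop. The documents support neither reading.

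What survives is the conflict. The uncapped sentence disagrees with the capped one in the same section, and the synopsis criterion is a different rule. Its toxicity term is not tied to the 16.1 definition. Read as an observed proportion, it is crossed at 22 of 70 (31.4%), whereas the posterior boundary at 70 is 27 (38.6%).

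A reader might also infer that more than 70 patients are certain to be treated. That is conditional: both cohorts must pass their first stage and fill, no safety stop may occur, and someone must be replaced. Section 9.1 says "Up to 70 evaluable patients will be enrolled on this study", and section 16.1 can be read as 70 enrolled in total. The second reading does not sit with the replacement rule in 9.1 and 9.4.

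Finally, measuring from n = 65 would make the gap look larger: at a true rate of 0.40 the share of unstopped trials would be 20%, 28% and 41%. That credits the change with a look at 70 that the cap already allows. Conditional shares at a true rate of 0.50 would mislead too, since 98.8% of trials have stopped by 70 and the gain is at most 1 point overall.

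**Conclusion.** The point holds in a limited form. The stated cap, the boundary table and the operating characteristics are set for at most 70 treated patients, while the plan's own enrolment rule allows more than 70 to be dosed and counted for toxicity. The documents contradict themselves on what applies after the 70th.

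The size is modest. Depending on the assumed replacement rate (10% to 30%), continuing the rule adds 1.8 to 7.9 points of stopping probability at a true rate of 0.40, 1.4 to 6.4 points at 0.35, 0.5 to 2.0 points at 0.30, and practically nothing at 0.20. These figures assume that both cohorts fill and that looks are every five patients, as Table 16.2 implies. The design is not invalidated, but the correction is cheap and concerns safety, so it should be made.

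**What to change.** - State in 16.1 that the existing posterior criterion counts every patient who receives at least one dose, including those later replaced, and runs until the last patient is enrolled.
- Extend Table 16.1 with the same prior and cut-off: 27/70, 29/75, 31/80, 33/85, 34/90, 36/95, 38/100.
- Recompute Table 16.2 for the expected number treated including replacements, and state the replacement rate assumed.
- Reconcile the synopsis toxicity stop, sections 9.1 and 9.4, the total of 70 in 16.1, and the capped and uncapped sentences of 16.1, so that one rule, one toxicity definition and one patient count apply throughout.

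The cost is a sentence or two, seven table rows and a rerun of the same software. The stated early-stopping probability at a true rate of 0.30 rises from 0.18 to about 0.20–0.21, partly because a look at 70 is now tabulated. At a rate of 0.20 it is unchanged at 0.016.

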16.2 Toxicity Evaluation

Protocol: ARO-005

Crenolanib has been well tolerated in studies including over 100 patients and toxicity patterns are relatively well understood.

16.3 Statistical and Analytical Plans

The primary end-point is overall response rate. The overall response rates in the two cohorts will be evaluated along with its 95% confidence interval. Analysis of secondary endpoints will be predominantly descriptive statistics and will be interpreted as being exploratory and hypothesis generating. Progression free survival (PFS) and overall survival (OS) will be estimated using the method of Kaplan-Meier. Cox regression models will be used to determine the relationship with the time-to-events (e.g. PFS and OS) and the potential prognostic factors. Exploratory logistic regression will be used to identify the prognostic factors that are significantly correlated with the response rate.

